2.7.1 Exposure to study treatment

For all analysis described in this section, the Safety Set will be used.

Duration of exposure

The *duration of exposure to study drug* is defined as the time interval from first (non-zero) dose of study drug administration to last study drug administration date (i.e. last known study drug administration date), and it will be calculated using the following formula:

Duration of exposure (days) = [(last date of exposure to the study drug) – (date of first administration of the study drug) + 1 day], where:

- ‘Date of first administration of the study drug’ is defined as the first date when a non-zero dose of study treatment is administered. For the sake of simplicity, the date of first administration of study treatment is referred to **start date of study treatment**.
- ‘Last date of exposure to the study drug’ is the date of last administration of this study treatment which is defined as the last date when a non-zero dose of study treatment is administered. This date will also be referred as **last date of study treatment**.

The duration of exposure includes the periods of temporary study drug interruption.

For patients who did not take any study drug, the duration of exposure is defined as zero.

The duration of exposure excluding the temporary study drug interruption will also be computed, only time interval where the drug was known to be taken will be considered. It will be computed using the following formula:

Duration of exposure excluding temporary study drug interruption (days) = Duration of exposure (days) – number of days during this time interval where the actual dose was zero.

Both the duration of exposure and duration of exposure excluding interruptions will be summarized as continuous variables and by days as <28, 28 to <56, 56 to <84, 84 to <140, 140 to <164 and ≥ 164 .

Percentage of exposure

The percentage of exposure is defined as $100 \times (\text{duration of exposure excluding interruptions}) / (\text{duration of exposure})$.

It will be summarized as a continuous variable and by the following categories as <20%, 20% to <40%, 40% to <60%, 60% to <80% and 80% to $\leq 100\%$.

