Patients will commence study treatment with EPO at 40,000 units once weekly. EPO will be provided as available in the respective country. The EPO must be self-administered via the subcutaneous route by the patient or competent personal. The patient will be instructed by the investigator to take the study drug as prescribed. All doses planned and prescribed to the patient and all dose changes including reasons for change during the study must be recorded in the eCRF.

During the regular study visits the investigator or pharmacist will administer to the patient an appropriate number of vials or prefilled syringes, respectively, depending on the local availability. The number of vials or prefilled syringes of each strength dispensed will be recorded in the Study Drug Dosing Log. All EPO medication (used and unused) returned by the patient will be counted and the sum entered in the study drug dosing log by the investigator or pharmacist at the study site.

The initial dose is 40,000 units given subcutaneously once a week. If increase in Hb is < 1 g/dL and total Hb is < 12 g/dL after 4 weeks, the dose will be increased to 60,000 units/week. If increase in Hb is ≥ 1 g/dL and total Hb is < 12 g/dL, patients will continue the current EPO dose. If Hb increase is ≥ 1 g/dL and total Hb is ≥ 12 g/dL, the patients will hold EPO dose (Table 4-1).

If after 12 weeks of treatment with EPO, Hb increase is < 1 g/dL and total Hb < 12 g/dL, the patient will discontinue EPO as the patient is not responding. These patients who do not respond to 12-week-EPO treatment will be switched to the combination for another period of 12 weeks. If Hb increase is ≥ 1 g/dL and total Hb is < 12 g/dL, patients will continue the current EPO dose. If Hb increase is ≥ 1 g/dL and total Hb is ≥ 12 g/dL, the patients will hold EPO dose (Table 4-1).

Instruction how to self-administer subcutaneous injections should be provided by the study personal.

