2.2 Data included in the analyses

Data will be collected on patients aged ≥ 18 years or older with low- and-int-1-risk MDS, randomized in 1:1 ratio to DFX+EPO or EPO alone. If after 12 weeks of treatment with EPO alone, Hb increase is < 1 g/dL and total Hb is < 12 g/dL, the patient will switch to combination therapy of EPO and DFX. The study treatment duration is 24 weeks.

As per the current protocol, no interim analysis is planned. All interim (if required) and final CSRs will have a documented medical review by [REDACTED].

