2.7.2.2 Erythropoietin

Similarly, the exposure to EPO will be summarized in the following way:

Cumulative dose (units/week) = sum of all (actual weekly dose *Z* (units/week) × duration of dose *Z* administration (week)); where *Z* is the specific dose level considered, e.g. 40,000 units/week.

The following formulae will be used to compute the average weekly planned and the average actual weekly doses.

1. *Average planned dose (units/week)* = sum of all (planned dose *Z* (units/week) × corresponding planned dose *Z* exposure) / overall drug exposure (weeks),
2. *Average actual dose (units/week)* = Cumulative dose (unit/week) / overall drug exposure (weeks).

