4.2.3 Date of last administration of study drug

The date of last administration of study drug is defined as the last date when a non-zero dose of study treatment EPO or EPO+DFX DT or EPO+DFX FCT is administered and recorded on the DAR of the CRF. The date of last administration of study treatment is referred to **end date of study treatment or last date of study treatment**.

Note: For patients either randomized to EPO+DFX DT or EPO+DFX FCT or for patients who switch to EPO+DFX DT or EPO+DFX FCT after 12 weeks, the end date of study treatment could be the last date when a non-zero dose of DFX DT or DFX FCT is administered since EPO is administered weekly and the patient may have received the EPO 6 days before the last non-zero dose of DFX DT or DFX FCT is given.

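### SAP 2.7.1 ends once-weekly EPO exposure on the day of the last injection, so an on-schedule 24-week course scores 162 days and misses the top duration category

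*SAP*

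**What the plan says.** SAP 2.7.1 computes duration of exposure for a study drug as "last date of exposure to the study drug) – (date of first administration of the study drug) + 1 day". The last date is the date of last administration, "which is defined as the last date when a non-zero dose of study treatment is administered". SAP 4.2.1 names DFX and EPO as the study drugs, and SAP 2.7.2 reports duration for each. The result is summarised as a continuous variable and "by days as <28, 28 to <56, 56 to <84, 84 to <140, 140 to <164 and ≥ 164".

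The two drugs have different dosing intervals. DFX is taken daily. For EPO, Protocol 6.1.1 says "Patients will commence study treatment with EPO at 40,000 units once weekly". SAP 2.2 adds: "The study treatment duration is 24 weeks".

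SAP 4.2.3 recognises the gap for patients who also take DFX, "since EPO is administered weekly and the patient may have received the EPO 6 days before the last non-zero dose" of DFX. It uses this only to explain why their overall treatment end date may be a DFX date.

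SAP 2.7.2.2 builds cumulative EPO dose as weekly dose times weeks at that dose, summed over dose levels. Average actual dose is then "Cumulative dose (unit/week) / overall drug exposure (weeks"). No separate definition of exposure is given there for a weekly drug.

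**The concern.** A weekly injection is meant to cover the seven days up to the next one. A rule that counts to the last administration date credits only one of the last seven days. The duration categories appear to be built around whole weeks of treatment (28, 56, 84 and 140 days, with the top one starting 4 days short of 168). A 6-day loss is therefore enough to push an on-schedule EPO patient below the category that matches the weeks covered.

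What is at stake is how the exposure tables read. EPO is the control treatment and the backbone of both arms. As written, complete EPO treatment would look incomplete, and in a combination patient EPO would look shorter than DFX over the same weeks. The same duration may also feed the cumulative dose.

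**Working it through.** **Inputs.** Duration = last date - first date + 1, and the category limits (SAP 2.7.1). EPO once weekly from 40,000 units (Protocol 6.1.1). Treatment for 24 weeks (SAP 2.2). Nominal end-of-treatment day 168, counting Visit 3 as Day 1 (SAP 4.2.11). Assumption: injections exactly 7 days apart from Day 1, so 24 injections in 24 weeks; the documents do not print that count.

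**The SAP's own 6-day gap.** Injection n falls on Day 1 + 7(n - 1). For n = 24 this is 1 + 161 = 162. The course covers 24 × 7 = 168 days, and 168 - 162 = 6, as SAP 4.2.3 says.

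**Duration and category.** By the formula, EPO duration is 7(n - 1) + 1 = 7n - 6 days, against 7n days covered.

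| Injections | Days by SAP 2.7.1 | Category | Days covered | Category |
|---|---|---|---|---|
| 4 | 22 | <28 | 28 | 28 to <56 |
| 8 | 50 | 28 to <56 | 56 | 56 to <84 |
| 12 | 78 | 56 to <84 | 84 | 84 to <140 |
| 20 | 134 | 84 to <140 | 140 | 140 to <164 |
| 24 | 162 | 140 to <164 | 168 | ≥ 164 |

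Daily DFX for 24 weeks scores 168 - 1 + 1 = 168, in ≥ 164. A patient who stopped EPO after injection 21 scores 141 days and shares a category with one who had all 24.

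**Sensitivity to spacing.** If injection 24 is one day late the score is 163; if two days late it is 164, which reaches the top category. A late patient can thus outrank a punctual one.

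**Cumulative dose, if the 2.7.1 duration is used in 2.7.2.2.** At a constant 40,000 units/week the formula gives 40,000 × (7n - 6)/7, against 40,000n injected. The shortfall is 40,000 × 6/7 = 34,286 units for every n, or 6/(7n) of the true total:

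- 24 injections: 925,714 against 960,000 (-3.6%)
- 12 injections: 445,714 against 480,000 (-7.1%)
- 4 injections: 125,714 against 160,000 (-21.4%)

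**Average dose.** With the same 162/7 = 23.14 weeks above and below the line, 925,714 / 23.14 = 40,000, which is correct. For a patient raised to 60,000 after 4 weeks, the true total is 4 × 40,000 + 20 × 60,000 = 1,360,000 and the true average 56,667. Crediting the first level with its full 4 weeks gives 160,000 + 60,000 × 134/7 = 1,308,571 (-3.8%), average 56,543 (-0.2%). Ending each level at its own last injection gives 40,000 × 22/7 + 60,000 × 134/7 = 1,274,286 (-6.3%), average 55,062 (-2.8%).

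**After the fix.** Last injection + 6 days = Day 168, so 168 days or 24.0 weeks, in ≥ 164; 960,000 units; average 40,000.

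**The case against.** The best defence is that SAP 2.7.1 says plainly what it measures, namely first to last administration. Adding the dosing interval is a different definition, and no printed figure is miscalculated. That is true, but the rule is applied to two drugs with different intervals and then sorted by limits that fit only the daily one.

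Second, SAP 2.7.2.2 speaks of a duration per dose level and does not say this equals the 2.7.1 duration. If EPO is recorded in the CRF by interval, 24 weeks at 40,000 gives 960,000, which is right. This stands: the cumulative error is conditional on reading the text with the only exposure definition supplied.

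Third, the combination arm's EPO categories are left to Module 7, and derivations to Module 8. Either could resolve the point. Nothing in the supplied text does so.

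Several stronger readings are tempting but not supported:

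- **That planned days without an injection would be removed as interruptions.** SAP 2.7.3 counts an interruption only for a zero dose reported in the CRF and does not treat a missing dose as zero.
- **That average weekly dose is inflated.** This needs units summed in the numerator and the 2.7.1 weeks in the denominator. SAP 2.7.2.2 does not prescribe that mix.
- **That no full-course patient can reach the top category.** A two-day slip is enough.
- **That the comparison of EPO between arms is distorted.** The shortfall is the same 6 days per patient in both.

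**Conclusion.** The point holds as a definitional flaw of modest size. SAP 2.7.1 understates EPO exposure by 6 days per patient. With on-schedule injections, a full course is reported as 162 days in 140 to <164, and courses of 4, 8, 12 and 20 injections also drop one category. This is firmest for patients on EPO alone. For patients still taking DFX, SAP 4.2.3 lets overall treatment end on the last DFX date, but that does not alter EPO exposure reported as a separate drug.

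The cumulative-dose understatement (-3.6% for 24 injections at a constant 40,000, proportionally more for early stoppers) applies only if the 2.7.1 duration is the one used in 2.7.2.2. Average dose at a constant level is right on that reading; in a titrated patient it may be slightly low.

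Only descriptive exposure tables are affected. The primary analysis does not use exposure. The correction is still worth making, because it is cheap and the present rule makes complete treatment look incomplete.

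**What to change.** - **SAP 2.7.1:** for EPO, define the last date of exposure as the last non-zero injection date + 6 days, capped at the end-of-treatment visit or death. Refer to the visit by name: SAP 4.2.5 defines end of treatment as the last day study drug was received, and a cap there would cancel the extension for patients on EPO alone.
- **SAP 2.7.2.2:** define cumulative EPO dose as the sum of units injected, labelled in units (weekly dose times weeks gives units, not units/week). Define average actual weekly dose as that sum divided by the corrected exposure weeks.
- **DFX:** leave unchanged.
- **Modules 7 and 8:** check that their categories and derivations match.

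The cost is a few sentences in the SAP and a small programming change. It needs no new data and alters no dosing rule.

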2.7.2 Dose exposure

For all analysis described in this section, the Safety Set will be used.

The dose exposure will be provided for both DFX and EPO in the following way:

- *For patients randomized to EPO and those who do not switch to combination after 12 weeks: Duration of exposure to EPO for 24 weeks.
- For patients randomized to EPO+DFX: Duration of exposure to EPO for 24 weeks (with suitable exposure categories described in RAP M7) and duration of exposure to DFX DT or DFX FCT for 24 weeks (duration unit expressed as number of days with suitable exposure categories described in RAP M7).
- For patients randomized to EPO and switched to combination after 12 weeks: Duration of exposure to EPO for 24 weeks and duration of exposure to DFX DT or DFX FCT for 12 weeks (week 13 to week 24).

Note: Patients randomized to EPO and switched to combination after 12 weeks, will not be counted in *. The patient population as described in * will be exclusively those patients who were randomized to EPO and remained in the EPO arm for 24 weeks.

2.7.2.1 Deferasirox

Exposure to DFX DT or DFX FCT will be summarized descriptively using the following parameters: average planned daily dose (mg/kg/day) and average actual daily dose (mg/kg/day).

The actual daily dose is calculated in the following way:

Actual daily dose per kg of weight (mg/kg/day) = actual daily dose (mg/day) / last available weight prior to the dose administration (kg)

The cumulative dose is calculated in the following way which is used later to calculate average actual dose.

Cumulative dose (mg/kg) = sum of all (actual daily dose *Z* (mg/kg/day) × duration of dose *Z* administration (days)); where *Z* is the specific dose level considered, e.g. 10 mg/kg/day for DFX DT or 7 mg/kg/day for DFX FCT.

The following formulae will be used to compute the average daily planned and the average actual daily doses.

1. *Average planned dose (mg/kg/day)* = sum of all (planned dose (mg/kg/day) × corresponding planned dose exposure) / overall drug exposure (days),
where the planned dose is the dose reported in the CRF page for a given time interval.
2. *Average actual dose (mg/kg/day)* = Cumulative dose (mg/kg) / overall drug exposure (days).

2.7.2.2 Erythropoietin

Similarly, the exposure to EPO will be summarized in the following way:

Cumulative dose (units/week) = sum of all (actual weekly dose *Z* (units/week) × duration of dose *Z* administration (week)); where *Z* is the specific dose level considered, e.g. 40,000 units/week.

The following formulae will be used to compute the average weekly planned and the average actual weekly doses.

1. *Average planned dose (units/week)* = sum of all (planned dose *Z* (units/week) × corresponding planned dose *Z* exposure) / overall drug exposure (weeks),
2. *Average actual dose (units/week)* = Cumulative dose (unit/week) / overall drug exposure (weeks).

2.7.3 Dose reductions and interruptions

The number of patients with dose reductions or interruptions, as well as the reasons leading to study drug dose reduction or to study drug interruption will be tabulated.

The number of dose interruptions and dose reductions will be tabulated by treatment group. Both of dose reduction and dose interruption will be calculated with regards to DFX DT or DFX FCT and EPO. Patients randomized to EPO arm or EPO+DFX arm may have an AE related to either EPO and/or DFX and thus the drug may be stopped or the dose may be reduced till the AE severity reduces.

An **interruption** is defined as a dose equal to zero on one or more days as reported in the CRF. A missing dose will not be considered as zero. A zero dose will not be considered as an interruption if it is the last dose administration record for a patient.

An interruption during consecutive days for the same reason is counted once.

If an interruption occurs for more than one consecutive day due to different reasons, then it will be counted for each reason.

A **dose reduction** is defined as a decrease in dose from the protocol planned starting dose or a decrease from the previous non-zero dose, even if this decrease has been directly preceded by an interruption. If, due to a dosing error, a patient receives higher dose than protocol planned starting dose and moves down to the planned starting dose then this is not be counted as a reduction. However if they move directly from a higher than planned starting dose down to a lower than protocol planned starting dose, then this is counted as a reduction.

A **dose increase** is defined as an increase in dose from the protocol planned starting dose or an increase from the previous non-zero dose, even if this increase has been directly preceded by an interruption.

2.8 Concomitant medication

For all analysis described in this section, the Safety Set will be used.

Concomitant therapy is defined as any interventions (therapeutic treatments, procedures or significant non-drug therapies) other than the study treatment administered to a patient coinciding with the study treatment period.

Concomitant or prior medications entered into the database will be coded using the World Health Organization (WHO) Drug Dictionary Enhanced (DDE) ATC term according to the latest version during the time of analysis of data.

In addition to categorizing medication data by preferred term, drugs are classified according to their ATC classification in order to present and compare how they are being utilized.

Concomitant medications and significant non-drug therapies taken concurrently with the study drug will be listed and summarized by ATC class, preferred term and treatment arm by means of frequency counts and percentages. These summaries will include medications starting on or after the start of study treatment or medications starting prior to the start of study treatment and continuing after the start of study treatment.

Any prior medications, procedures or significant non-drug therapies starting and ending prior to the start date of study treatment will be listed.

2.9 Efficacy evaluation

2.9.1 Primary objective

The primary objective will be to assess the effect of treatment with DFX+EPO vs. EPO alone on erythropoiesis after 12 weeks of treatment.

2.9.1.1 Variable

The primary variable is the difference in proportion of patients achieving an erythroid response after 12 weeks of treatment between the two arms according to modified IWG 2006 criterion (increase in Hb from baseline ≥ 1.5 g/dL).

Patients meeting the criterion at any time within the first 12 weeks period will be considered erythroid responders.

2.9.1.2 Statistical hypothesis, model, and method of analysis

A patient is defined as an erythroid responder if the criterion of Hb increase from baseline ≥ 1.5 g/dL is met at any time within the first 12 weeks period.

Baseline is defined as the last available value within windows of 4 weeks prior to or on treatment start date. No imputation will be performed for missing Hb value.

Difference in proportions between treatment groups with its 95% Agresti-Caffo (Agresti-Caffo 2000) confidence interval will be provided. Erythroid response proportion will be also summarized by treatment group with its 95% Clopper-Pearson confidence intervals (Clopper and Pearson 1934). Analysis will be performed on FAS.

